- 2) Examine the change of health status of parent participants over time as a result of the 12-month (16 weekly, 3 biweekly, and 6-monthly session) DPP adult sessions through the evaluation of metabolic, physical fitness, and health habit parameters.

3. Study/Project Population,

Potential subjects and their parents will be informed of the study through flyers, community events, and physician referrals. Flyers will be distributed/posted at all YMCA sites and physician offices and clinics, throughout Memphis.

Inclusion criteria for youth participants will include:

- 1) Between 7-15 years-old
- 2) Hemoglobin A1C 5.7-6.4% or BMI \geq 85th percentile, parent **or** grandparent with pre/type II Diabetes
- 3) Able to participate in physical activity
- 4) Parent or caregiver participation

Exclusion criteria for youth participants will include:

- 1) Pregnant females
- 2) Those with mental health illness (e.g. depression, ADHD, etc.)
- 3) Medications that would interfere with testing results (e.g. metformin, insulin)

Inclusion criteria for parent participants will include:

- 1) ≥18 years-old
- 2) At least one child enrolled in ISC
- 3) Able to participate in physical activity

Exclusion criteria for parent participants will include:

- 1) Those with mental health illness (e.g. depression, ADHD, etc.)
- 2) Medications that would interfere with testing results (e.g. metformin, insulin).

Inclusion and exclusion criteria will be assessed via parent and child self/physician referral form. The UTHSC/LBCH subcommittee will approve all procedures for the Use and Protection of Human Subjects. ISC and control group participants will be assigned on a fist come first serve basis.

Consenting and Questionnaires:

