On the day of registration, parents or guardians will receive project information packets from the trained research team. The packets will include a parent/guardian consent form, a child assent form, and detailed participation requirements, benefits, and incentives. Once the researcher consents the parent and assents the child face-to-face, the child and parent will be asked to sit with the researcher to complete the study questionnaires. The parent will complete the Healthy Habits Questionnaire (parent version), the child and parent will complete the Healthy Habits Questionnaire (child version), and the child (child version) and parent (parent version) will complete the mental health questionnaire separately. Trained research team members will complete all face-to-face consenting and surveys/questionnaires. Upon consenting the family (parent and child/children) will be assigned, to either the ISC. Once completed the participant will return the following week to complete their pre-evaluation assessment.

The parents will be encouraged to contact the research team if they should have any questions regarding the study procedures. All questionnaires, consents, and assent forms must be completed prior to the data collection days with the assistance of a research team member. The research staff will review all materials and assign a study id prior to the child's participation in data collection. Following completion of the project parents or guardians of all children enrolled in the project will receive a report of their health behaviors, physical fitness, and mental health performance with strategies to improve/maintain their outcomes. The research team member will also inform the parent and child that video recording and pictures of the educational sessions, physical activity sessions, and evaluation sessions (only physical fitness measures) will be taken by a research team member for the use of dissemination and presentations regarding the findings. If parents do not wish to consent and child does not wish to assent to video recordings or photography of this nature the research team will make a note and respect the participants' wishes.

4. Research Design,

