This project will employ a quasi-experimental non-control group design with an intervention group (ISC). The intervention group will receive the ISC curriculum, which promotes healthier physical activity, nutrition, sleep, and stress coping practices. The intervention phase will consist of 12-months: registration, six evaluation sessions (2-3 hours per evaluation: Week 1, 8, and 16, 6-month, 9-month, and 12-month), and 16-weekly, 3-bi weekly, 6-monthly educational and physical activity sessions (1.5 hours per session: 45-minutes of health education and 45-minutes of physical activity). Youth between the ages of 7-15 throughout Shelby County will be recruited to participate in this study. Recruitment, data collection, and program implementation will be accomplished through a community-academic partnership between UTHSC/LBCH and the YMCA. Upon obtaining parental consent and child assent, all data collection will occur at the Gaisman Community Center site under the supervision of UTHSC/LBCH staff.

Incentives

Pre, post, and follow-up evaluations: \$50 gift card for participant

Programs sessions: attendance raffle: participants will be provided with a raffle ticket for attending sessions and will be able to select a n item for a prize box (water bottles, t-shirts, jump ropes, hand sanitizer, myPlates, etc.)

5. Study/Project Procedures

Research and Program Setting. The YMCA of Memphis & the Mid-South's mission is to put faith-based principles into practice through programs that build healthy spirit, mind, and body while strengthening communities. The YMCA is the largest provider of before/after school services serving children in the Shelby County, Tennessee and Desoto County, Mississippi School Districts, and selected schools in the

Marion School District in Marion, Arkansas; thus being a major provider of after school care in the Mid-South.

All data collection and program activities with youth and their families will be located at the Gaisman Community Center. All tests and program activities will be under the supervision of UTHSC/LBCH and YMCA staff by trained researchers and staff.

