- 2) Examine the change of health status of parent participants over time as a result of the 12-month (16 weekly, 3 biweekly, and 6-monthly session) DPP adult sessions through the evaluation of metabolic, physical fitness, and health habit parameters.
- 3) Examine the differences over time in metabolic, physical fitness, and health habit parameters among participants in the ISC group versus those in educational control group.

23.0 (1200) Site and Research Procedure Information

*Please list all sites and research procedures that will occur at each site. Research Site(s): If any of the following activities are being done, then include the site(s) below: identification of participants through review of their medical records; recruitment of participants; consent of participants; performance of screening procedures; interventions or interactions with participants; follow-up visits; collection of private information about participants; specimen storage; etc. Note: If any

activities are being conducted at any of the following: CRC, Methodist/Le Bonheur, Regional One Health, or University Clinical Health, review the corresponding institution's guidelines prior to submitting your application. The website listing the institution's point of contact is posted under the "Ouestion Mark" icon to the right.

Site Name and Address		Additional Site Information include suite #	
Institution: Other		YMCA [name]	Program staff training will be conducted at this site.
Institution: University of Tennessee - Health Science Center		CFRI-[name]	All consenting, data collection, data storage, data input and analysis will be at this site.
		Gaisman Community Center, [name]	ISC and WSC programs will be in held at this site.

23.2	* Is this a multicenter study/project (one that is conducted across many institutions in the U.S. or in the world and usually
	run by one sponsor)? Select "Not Applicable" if you are using a HUD, or engaging in treatment use of an unapproved
	drug/biologic or device, emergency use of an unapproved drug/biologic or device, or compassionate use of an unapproved
	device.

🔘 Yes. This is a multicenter study/proje	О.	Yes.	This	is a	multicenter	study	/projec
------------------------------------------	----	------	------	------	-------------	-------	---------

- No. This is NOT a multicenter study/project.
- Not Applicable.

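### The documents disagree on whether there is a control group; if there is one, the only allocation rule is arrival order, applied at consent before the pre-evaluation, so the Aim 3 comparison is predictable and may be confounded with enrolment time

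*Combined protocol and SAP*

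**What the plan says.** **Text that implies a control group**
- Section 21.1 item 3 (Study/Project Population), closing sentence: "ISC and control group participants will be assigned on a fist come first serve basis".
- Section 21.1 item 3 (Consenting and Questionnaires): "Upon consenting the family (parent and child/children) will be assigned, to either the ISC". The sentence stops there; the alternative to ISC is never named.
- Section 22.1, the third of the specific aims listed there: "Examine the differences over time in metabolic, physical fitness, and health habit parameters among participants in the ISC group versus those in educational control group".
- Section 23 (site table): "ISC and WSC programs will be in held at this site". WSC is not defined, so whether it is the control programme cannot be told.

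**Text that implies none**
- Section 21.1 item 4 (Research Design): "This project will employ a quasi-experimental non-control group design with an intervention group (ISC", followed by a description of that one group only.
- The synopsis (section 21.1 item 2) lists two aims, one for youth and one for parents, and neither is comparative.
- The visit schedule in section 21.1 item 5 contains only ISC sessions, and a parent qualifies only through a child enrolled in ISC (sections 21.1 item 3 and 27.1).
- Neither analysis statement (section 21.1 item 6; section 34.3) contains a group term or a group-by-time term.

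**Timing.** After consent, "the child and parent will be asked to sit with the researcher to complete the study questionnaires" at the registration visit. Then: "Once completed the participant will return the following week to complete their pre-evaluation assessment". The pre-evaluation (Visit 2) covers physical activity, fitness and health measures.

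**The concern.** Wherever the documents contemplate a control group, the only way of forming it is order of arrival. No other allocation method appears, nor any ratio, group size, fill order or concealment. This has two consequences.

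1. **Predictability.** Anyone who knows the rule and how many places are taken can foresee the next assignment. A family's registration can then be hurried or delayed to suit. Assignment at consent also puts the group decision before the pre-evaluation, so the physical, metabolic and accelerometer baselines are taken from families who may already know their group, and some may not return for them.
2. **Confounding with enrolment time.** Recruitment mixes flyers, community events and physician referral, and the study is to last 5 years including analysis, against 1 year of participation per subject. Early and late families could differ in motivation, referral route and season. If one group fills before the other, group and enrolment period do not overlap. Aim 3 could then show or hide a benefit for reasons unrelated to the programme, and a larger sample would not help. The listed covariates (race, ethnicity, SES, age, and BMI-Z or grade) include neither enrolment date nor referral route.

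**Working it through.** The documents give no alpha, power, effect size, SD, ratio or dropout for Aim 3, so there is no figure of the plan's own to reproduce. What follows is an illustration.

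**Input from the documents.** Section 24.1 gives a local accrual of 100, including screen failures and withdrawals, with age range 7-15 and 18+. Children and adults are counted together, so there are fewer than 100 children. No split by group is stated.

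**Assumptions, not from the documents.** 50 children, 25 per group; a two-sided 5% test of 12-month change; no true effect; change correlates r with arrival rank; children treated as independent.

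**Case 1: one group filled first.** Put arrival rank on 0 to 1. Its SD is 1/√12. The first half has mean 0.25 and the second half 0.75, a gap of 0.5, which is 0.5 × √12 = 1.73 rank SDs. Hence:

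spurious difference = 1.73 × r SD

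Simulation, 20,000 replicates per cell:

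| r | Spurious difference (SD) | Rejection, 25 per group | Rejection, 20 per group |
|---|---|---|---|
| 0.1 | 0.17 | 9.1% | 8.6% |
| 0.2 | 0.35 | 22.8% | 18.9% |
| 0.3 | 0.52 | 46.0% | 37.6% |

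Check by formula at r = 0.2 and 25 per group: SE = √(2/25) = 0.283; 0.346/0.283 = 1.22; Φ(1.22 − 1.96) + Φ(−1.22 − 1.96) ≈ 0.23, in agreement. Under random allocation, 25 per group, the mean difference is about 0 and rejection is 4.5-5.2%.

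**Same case, stated as a trend.** Let D be the rise in the change score, in SD, from first to last enrolled. The bias is D × 25/49 ≈ 0.51D with 25 per group. D = 0.2, 0.5 and 1.0 gives about 0.10, 0.25 and 0.51 SD and type I error of 6.5%, 15% and 44%. With 50 per group, a ceiling since adults are in the 100, the type I errors are 8%, 24% and 71%.

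**Case 2: strict alternation by arrival.** The mean positions differ by 1/49 = 0.02, so at D = 1.0 with 25 per group the bias is 0.02 SD and type I error is 5.1%. The time-trend bias is almost gone, but the next assignment is still known.

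**Case 3: drift in baseline level only.** If later families start from a different level but change at the same rate, a comparison of change cancels the drift. Simulated with 50 per group filled sequentially: bias 0.005 SD, type I error 4.9%. Only drift in the amount of change produces the Case 1 bias.

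**The case against.** The strongest reply is that there is no control group. The Research Design paragraph says so, the synopsis aims and visit schedule agree, and no model has a group effect; the control sentences look like remnants of a two-arm plan. This stands as a reason to settle the design first. It does not dispose of the point, because Aim 3 and the assignment sentence are current text, and following them would produce the comparison described.

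Three stronger readings are tempting, and the documents do not support them:

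- **That Aim 3 is certainly confounded with early versus late enrolment.** This needs one group to fill first. That is a natural reading of first come, first served, but no fill order is stated, and alternation would nearly remove the trend bias.
- **That assignment precedes all baseline data, so families could leave having given none.** The Healthy Habits and mental health questionnaires are completed at the registration visit and may come before assignment; their order is not stated. Only the pre-evaluation measures clearly follow it. Nor do the documents say when families are told their group.
- **That non-random allocation is concealed from the reader.** The study calls itself quasi-experimental. That discloses the absence of randomisation, but does not supply a fill rule, concealment or any handling of enrolment date.

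The simulation also ignores that families are assigned together, so its rejection rates are approximate.

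**Conclusion.** The point holds conditionally. The four places that bear on the control group (sections 21.1 items 3 and 4, including the consenting paragraph, and 22.1 aim 3) contradict each other and must be reconciled. If a control is kept, the stated rule is defective and not merely under-described: arrival order at consent is predictable to staff who know it, precedes the pre-evaluation, and leaves the Aim 3 difference open to confounding with enrolment time.

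The size depends on the unstated fill order. Under assumed sequential filling with 25 children per group, the bias is 1.73r SD, with type I error of about 9%, 23% and 46% at r = 0.1, 0.2 and 0.3. Under strict alternation the time-trend bias is near zero, and predictability is what remains. The group size, r, alpha and fill order are all assumptions.

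**What to change.** Choose one design and make every section follow it.

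**(a) Keep the control.**
- Replace the assignment sentence in section 21.1 item 3 with: *Families (parent and all enrolled children together) will be assigned 1:1 to ISC or educational control from a computer-generated list with randomly varying block sizes, prepared and held by the Biomedical Informatics Core. Each assignment will be released only after the family has completed the pre-evaluation.*
- Amend the consenting paragraph so that assignment follows the pre-evaluation, and amend the Research Design paragraph to describe two groups. Align the synopsis aims and the parent eligibility criterion.
- Analyse Aim 3 with each health measure as the outcome and a group-by-time term, allowing for clustering within families. Randomising without this would leave Aim 3 unanalysed.
- First come, first served may still decide who is admitted to the study, but not which group they join.

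**(b) Drop the control.** Delete the assignment sentence, repair the consenting sentence by removing its either, delete Aim 3 from section 22.1, and report no between-group effect.

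**Cost.** Both options need a protocol and IRB amendment. Option (a) adds one allocation list from a core that section 36.1 says already supports statistical design. Families can no longer be promised ISC for signing up early, and they learn their group about a week later. Because no control programme is described anywhere, option (a) also requires one to be written down; the documents do not allow that cost to be estimated.

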The YMCA will collaborate and commit to the following throughout this study: 1) assist the research team to identify the cohort of children, 2) identify the staff members who will be trained to deliver the weekly lessons, 3) make the arrangements for staff training and development, and 4) provide administrative and financial oversight support to site directors and study staff. This collaboration is a mutually agreeable effort as it will result in gained scientific knowledge about factors that influence youth well being in Memphis. The expansive footprint of the YMCA and its own involvements with various populations in the community provides many opportunities for community translation of the research findings. Nationally, YMCAs are forging relationships and seeking ways to engage underrepresented racial and ethnic populations with close relations established with the Hispanic and African-American communities. The Department of Human Services licenses all facilities of the YMCA; most program sites are located in school cafeterias and have access to outdoor playgrounds, computer laboratories, and school classrooms. The staff ratio is maintained at 1 staff: 12 participants, with two staff members present at all times. Annually, staff members are provided 20-25 hours of in-service training to include: first aid, CPR/blood borne pathogens, child abuse prevention, stewards of children, and sexual harassment. Through the study collaboration staff will receive an additional 40-50 hours of training and continued education. All data collection and program activities will occur on YMCA sites under the supervision of UTHSC/LBCH. In total, 1-2 hours will be required to complete all measures during the evaluation sessions. Youth will be provided with healthy snacks and beverages throughout the testing period, and will be encouraged to take breaks as needed. Each curriculum session will last 1.5 hours and lessons will be taught by the YMCA trained Life Coaches under the supervision of a research team member.

Data Collection Evaluation Days.

Prior to the initial pre-evaluation a registration/consent day will be offered. Research staff will consent parents, assent children, and sit face-to-face with the parent and child to complete the Healthy Habits and mental health questionnaire. On evaluation days the participants will rotate through stations to complete all the measures collected by the research team members.

Questionnaires:

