Physical Activity. An accelerometer (Computer Science and Applications, Inc., Shalimar, FL), will be used to assess physical activity (Epistein, 1996; Sallis 1990) The child will be asked to wear the accelerometer for 7-days. To ensure good reliability of devices use the children and parents will be taught how to use the accelerometers during a home visit and reminded of wear via a phone call. The PI and a research team member will schedule and conduct the home visits (pick-up and drop-off) with the parent and child. The home visits will provide an opportunity for detailed instruction and demonstration of device use as well as provide accountability of the device. The home visits will take approximately 30 minutes to complete. Metabolic Parameters. The metabolic parameters will take approximately 30 minutes to complete and will be administered by a trained health specialist under supervision of a medical director. The Inbody-570 multi-frequency bioimpedance analyzer (Biospace, Beverly Hills, CA), will be used to assess body composition (Inbody 570, 2006.) Information recorded will include: body weight, percent body fat, and BMI. Height (centimeters) will be measured using a Weigh Beam Eye-Level physicians' scale in cm (DETECTO, Webb City, MO, USA). A portable anthropometer (Lafayette Instrument Company, Lafayette, IN) will be used to measure sagittal abdominal height (SAH), as a predictor of visceral abdominal fat(Sampaio, 2007.) A Gulick spring loaded measuring tape (Dunlee, Aurora, IL) will be used to indicate central obesity (Center of Disease and Control, 2012.) Systolic and diastolic blood pressure (SBP and DBP respectively) will be taken using a manual sphygmomanometer (blood pressure cuff) with a child's cuff placed over the brachial artery (Tycos Instruments Inc., Arden, NC) using standard procedures (Kirkenale, 1967.) Resting heart rate will be measured manually after five minutes of seated rest through palpating radial pulse over 60 seconds and will be recorded as beats per minute (American Heart Association, 1996.) A1C will be assessed from a fingerstick capillary whole-blood sample using an A1CNow device (John & Edwards, 1994) (PTS Diagnostics, Indianapolis, IN). Lipid profile will measure total cholesterol, triglycerides, and LDL and HDL levels using Cholestech LDX (Alere, San Diego, CA.) Physical Fitness. The physical fitness assessments will take approximately 1 hour to complete and will be administered by a trained research staff under supervision of an exercise physiologist. The National Institute of Health's (NIH) two-minute walk test will be used to measure aerobic endurance (NIH, 2012). A Jamar plus handgrip dynamometer (Sammons Preston, Bolingbrook, IL) will used to measure grip

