Physical fitness (cardiorespiratory, muscular strength and endurance, and motor skills): The fitness battery will include the NIH two-minute walk test (aerobic fitness), handgrip strength, wall-sit (lower body strength), push-ups (upper body strength), curl-ups (abdominal strength), unilateral balance, 50-foot shuttle run (agility), and sit-and-reach box (lower body flexibility).

Metabolic Parameters (total and central adiposity, blood pressure, physiological stress): These measures include the Inbody-570 multi-frequency bioimpedance analyzer (body composition), Weigh Beam Eye-Level physicians' scale (height), anthropometer (sagittal abdominal height), Gulick spring loaded measuring tape (central obesity), sphygmomanometer (systolic and diastolic blood pressure), radial pulse (resting heart rate), A1C (blood glucose levels) and lipid profile (total cholesterol, triglycerides, and LDL and HDL levels.)

Health Habits (physical activity, nutrition, self-efficacy): Self-report measures will include knowledge, physical activity, sedentary habits, nutrition, and stress management.

Mediators: A parent- and child-report healthy habits questionnaire (adapted from previous research) will be used to assess demographics (i.e. age, race/ethnicity, SES, home environment), child's academic status, family health history, weight perception, and frequency and range of typically consumed foods, exercise, sleep, and healthy-lifestyle behaviors.

Analysis: We will use mixed repeated measures ANOVA model time as the outcome and physical fitness, metabolic parameters, and health habits as our predictor variables. We will also include possible covariates (race, ethnicity, SES, age, and BMI-Z) in the models.

22.0 (1075) Background & Current Status of Work in the Field

22.1 * Provide a discussion of the background and current status of work in the field.

* This section must provide a justification and rationale for conducting the study/project.

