Persons	Who Are Institutionalized as Mentally III	
☐ Students	s of a School Associated with this Project	
☐ Employe	ees of an Institution/Agency Associated with this Project	
Dl1-:		
Please explai	in how a certain category of vulnerable subjects might be incidentally included:	
26.0 (14	194) Study/Project Duration	
26.1 * Wha	at is the anticipated duration of a single subject's participation in the study/project?	
	ar is the material and money a surged of participation in the setting, projects	
1 year		
26.2 * How	v long will the entire study last locally, including time for data analysis?	
5 years		
27.0 (15	500) Inclusion Exclusion Criteria	
27.1 Identi	fy inclusion criteria.	
Order		
Number	Criteria	
1	1) Ages 7-15	
	Parent Inclusion Criteria: 18 and older	

1	
2	2) Prediabetes-A1C 5.7-6.4% ${f or}$ BMI of an 85th percentile or above ${f or}$ a grandparent /parent with diabetes
2	Parent Inclusion Criteria: at least one child enrolled in ISC
3	3) Able to participate in physical activity
3	Parent Inclusion Criteria: Able to do physical activity
4	4) Parent enrolls in the adult DPP

27.2 Identify exclusion criteria.

Order Number	Criteria
1	1) pregnant females
1	Parent Exclusion Criteria: those with mental disorder (e.g. depression, ADHD, etc.) and/or severe mental illness which requires immediate treatment (e.g., active psychotic episode)
2	2) those with mental disorder (e.g. depression, ADHD, etc.) and/or severe mental illness which requires immediate treatment (e.g., active psychotic episode)
3	3) medications that would interfere with testing results (eg. metformin, insulin)
3	Parent Exclusion Criteria: medications that would interfere with testing results (eg. metformin, insulin)

28.0 (1600) Subject Selection and Recruitment					
28.1 * How will subjects be selected?					
* Subjects identified through medical record screening					
⊙ Yes ○ No					
* Contact by investigator with his/her patients in the clinical setting					
⊙ Yes ○ No					
* Referral from non-investigator practitioner					
⊙ Yes C No					
* Subjects recruited from among students and/or employees					
O Yes ⊙ No					
* Telephone pre-screening					

* Website pre-screening	
C Yes No	
* Advertising	
* Other	
O Yes O No	
28.2 * Recruitment Materials	
At the end of this application, you are required to attach all recruitment materials which you intend to use for this study /project.	

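### Only a child's cuff is named for blood pressure and no cuff-selection rule is given, although parents aged 18+ and youth who may be overweight are measured; followed as written, readings may be biased by an amount that shifts with arm size.

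*Combined protocol and SAP*

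**What the plan says.** Section 21.1, item 5 (Evaluation Measures, Metabolic Parameters) has systolic and diastolic pressure taken with a manual sphygmomanometer "with a child's cuff placed over the brachial artery", "using standard procedures", with a literature citation. The outcome list in item 6 repeats the instrument, "sphygmomanometer (systolic and diastolic blood pressure", without cuff detail, and so does Section 34.3.

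The people measured are of very different sizes:

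- The second specific aim concerns parents and the "DPP adult sessions through the evaluation of metabolic, physical fitness, and health habit parameters". Parents must be 18 or older.
- Youth are aged 7 to 15. One of their three alternative entry routes in Section 27.1 is a "BMI of an 85th percentile or above".
- On evaluation days "the participants will rotate through stations to complete all the measures". No separate adult procedure is described.

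Item 4 (Research Design) plans "six evaluation sessions (2-3 hours per evaluation: Week 1, 8, and 16, 6-month, 9-month, and 12-month". The mid-evaluation omits only blood glucose and cholesterol, so blood pressure is due at all six. The same section states: "This project will employ a quasi-experimental non-control group design with an intervention group (ISC".

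**The concern.** One named cuff size faces arms ranging from a 7-year-old's to an adult's. As a general measurement principle, which the documents do not discuss, a cuff too small for the arm tends to read high. A constant error would raise the level but drop out of a within-person change. An error that depends on arm circumference need not drop out, because circumference can change during the year: youth grow, and the programme targets body composition.

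Both aims concern change over time, and blood pressure is among the metabolic parameters in each. An arm-size artefact could be read as a programme effect, or could hide one. If neither arm circumference nor cuff size is recorded, the problem cannot be diagnosed or corrected afterwards. Informal switching of cuffs between visits would add a further shift that nobody could trace.

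**Working it through.** The plan gives no blood pressure target, SD, effect size, power or cuff-error figure, so there is no stated result to reproduce. The check is mainly textual, followed by one illustration on assumed values.

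**Step 1: is another cuff or a selection rule given anywhere?** Section 21.1 item 5 names a child's cuff. Item 6 and Section 34.3 name only the sphygmomanometer. The visit descriptions in Sections 21.1 and 30.1 refer back to the measures already described. No section mentions an adult or large cuff, arm circumference, or a record of the cuff used.

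**Step 2: would the design or the model remove an arm-size error?**

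- The Research Design text has no control group. Section 22.1 lists a third aim against an educational control group, and item 3 of 21.1 mentions control assignment, so the documents are not consistent. Even a concurrent control would remove only the growth-related drift common to both groups, not drift caused by weight change that differs between them.
- Item 6 lists race, ethnicity, SES, age and BMI-Z as covariates. Section 34.3 lists race, ethnicity, SES, age and grade. Neither includes arm circumference or cuff size. BMI-Z is at most a partial proxy: a child can stay at the same BMI-Z while the arm grows.

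**Step 3: illustration.** All inputs are assumed:

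- error slope: 0 to 2 mmHg per cm of arm circumference
- arm change over 12 months: 0.5 to 2 cm
- SD of blood pressure change: 8 to 12 mmHg
- n analysed: 50 to 100. Section 24.1 gives an accrual of 100, including parents, screen failures and withdrawals, so 100 is an upper limit.

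Spurious shift b = slope × arm change. The smallest is 0 × 0.5 = 0 mmHg and the largest is 2 × 2 = 4 mmHg.

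The chance of declaring a change when there is none, for a paired z-test at two-sided 0.05, is 1 − Φ(1.96 − t) + Φ(−1.96 − t), with t = b / (SD/√n).

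Example: b = 2, SD = 12, n = 50. SE = 12/√50 = 1.70 and t = 2/1.70 = 1.18, giving about 0.22. With SD = 8 and n = 100, SE = 0.80 and t = 2.5, giving about 0.71.

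| Shift b (mmHg) | n = 50, SD 12 | n = 50, SD 8 | n = 100, SD 12 | n = 100, SD 8 |
|---|---|---|---|---|
| 0 | 5% | 5% | 5% | 5% |
| 0.5 | 6.0% | 7.3% | 7.0% | 9.6% |
| 1 | 9.1% | 14.3% | 13.3% | 24.0% |
| 2 | 21.8% | 42.4% | 38.5% | 70.5% |
| 4 | 65.4% | 94.2% | 91.5% | 99.9% |

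The table treats the shift as a net shift in one direction across everyone analysed. In youth, growth and weight loss pull in opposite directions, so the net value may be nearer the top of the table than the bottom.

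**The case against.** A reader might infer that the plan prescribes a child's cuff for every participant, parents included, and that the readings are therefore known to be biased. The documents do not support this, for four reasons.

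- The text never says which cuff parents get. Nearby wording, such as the accelerometer instructions, is about the child, so the sentence may describe only the youth procedure.
- The reference to standard procedures may cover cuff choice. The cited source cannot be consulted here. The metabolic measures are also taken by a trained specialist under a medical director, who might not accept a badly fitting cuff.
- There are no arm sizes, cuff dimensions or error figures. Nothing shows that the cuff is too small for a given youth, and raised BMI is only one route of entry.
- Because growth and weight loss oppose each other, a claim that the programme would produce a spurious fall goes too far.

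All four points stand as limits on certainty and size, but they do not remove the gap. If the sentence covers children only, an Aim 2 outcome has no stated cuff at all. One child's cuff for ages 7 to 15, with overweight as an entry route, is still too narrow a specification. If the cited standard does require sizing by arm, it conflicts with the single cuff named in the same sentence, and the two must be reconciled.

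**Conclusion.** The concern holds in conditional form. The plan names one small cuff, offers no alternative or selection rule, and measures blood pressure in adults and in youth who may be overweight. Followed as written, this will tend to give high readings on larger arms, with an error that may change over the 12 months and that the stated design and covariates cannot separate from true change.

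The size and net direction are unknown. On the assumed inputs the artefact is about 0 to 4 mmHg, which ranges from harmless to enough to produce a false finding more often than not. The conclusion rests on two things outside the documents: the general principle that an undersized cuff reads high, and some change in arm size during follow-up. Blood pressure is one item in a long battery and is not singled out as primary. This is a change the sponsor should make; it does not undermine the study as a whole.

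**What to change.** In Section 21.1 item 5, replace the reference to a child's cuff with a cuff selected from mid-upper-arm circumference measured at each evaluation, and state that this applies to youth and parents alike. Record the arm circumference and the cuff size used on the data form, so that any remaining dependence on arm size can be examined.

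The cost is a revised sentence, two extra data fields, a set of cuff sizes, and one more tape measurement per participant per evaluation. The spring-loaded tape already listed for central obesity can be used.
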